### **Screening Evaluation**

A history and physical examination, including performance status evaluation, height, weight, and vital signs, should be performed within 28 days prior to the first dose of TAK228.

The following laboratory studies should be performed within 3 days prior to the first dose of TAK228 – CBC with differential, Serum chemistries – sodium (Na), potassium (K), chloride (Cl), glucose, bicarbonate (CO2), blood urea nitrogen (BUN), creatinine (Cr), calcium (Ca), magnesium (Mg), phosphorus, total protein, albumin, alkaline phosphatase, aspartate transaminase (AST), alanine transaminase (ALT), total bilirubin, direct bilirubin, uric acid, lactate dehydrogenase (LDH), Beta-2 microglobulin, prothrombin time (PT/INR), partial thromboplastin time (PTT), hemoglobin A1c, and urine analysis, and a fasting serum glucose, triglycerides, cholesterol panel, and serum Beta-HCG in women of child-bearing potential. Fasting is defined as nothing to eat for at least 4-6 hours before blood draw.

ECHO or MUGA performed.

Quantitative immunoglobulins (IgG, IgA, and IgM) within 28 days prior to the first dose of TAK228.

HIV 1 and 2 antibody, Hepatitis C viral antibody, Hepatitis B surface antigen, Hepatitis B core antibody within 28 days prior to the first dose of TAK228.

The following staging studies should be performed within 28 days prior to the first dose of TAK228 – CT scans of neck, chest, abdomen, and pelvis; Chest X-ray – PA and lateral; and unilateral bone marrow biopsy and unilateral bone marrow aspirate. An optional PET/CT scan may be obtained within 28 days prior to the first dose of TAK228 at the discretion of the treating physician.

An electrocardiogram will be obtained within 28 days prior to the first dose of TAK228.

For correlative studies, an optional 10 ml of blood sample [2 heparin containing green top tubes (5 ml/tube)] will be collected within 3 business days prior to the first dose of TAK228. These samples will be transported within 4 hours of collection to the RPPA Core Laboratory Facility and/or Lymphoma Tissue Bank, depending on time of collection, at M. D. Anderson Cancer Center (MDACC). Blood from green top tubes will be processed for isolation of peripheral blood mononuclear cells (PBMC) using standard laboratory protocols.

For correlative studies, an optional archival tumor FFPE biopsy material collection will be occur for analysis of mutations in MTOR.

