#### **EVALUATION DURING STUDY**

During the first cycle, patients will be evaluated by the treating physician in the clinic prior to the start of TAK228 (within 3 business days). A relevant history and physical examination, including performance status evaluation and vital signs, will be recorded within 3 business days of the first dose of TAK228. Patients will subsequently be assessed by the medical team on days 8, 15, and 22 (within 3 business days). At these weekly assessments, a relevant history and physical examination will be recorded. Toxicities will be graded according to the NCI CTC v4.0 during these visits.

For all cycles beyond cycle 1, patients will be evaluated by the treating physician in the clinic prior to each cycle of TAK228 (within 3 business days). A relevant history and physical examination, including performance status evaluation and vital signs, will be recorded within 3 business days of each dose of TAK228. Toxicities will be graded according to the NCI CTC v4.0 during these visits

The following laboratory studies should be performed within 3 business days prior to each cycle of TAK228 – CBC with differential, Serum chemistries - Na, K, Cl, CO2, BUN, Cr, Ca, Mg, phosphorus, total protein, albumin, alkaline phosphatase, AST, ALT, total bilirubin, direct bilirubin, urinalysis, uric acid, PT/PTT/INR and LDH, and a fasting serum glucose, triglycerides, cholesterol panel, and serum Beta-HCG in women of child-bearing potential.

During the first 2 cycles of therapy, patients will monitor their glucose at least once daily in a fasting state via a provided glucometer. All patients will self monitor their glucose daily in a fasting state approximately the same time each day, and if directed by the clinical trial team may require monitoring more than once per day. If no irregularities in the fasting blood glucose level are observed during a minimum of 2 consecutive months, then the frequency of in-home fasting blood glucose testing can be reduced to a minimum frequency of once weekly, depending on the investigator's judgement and approval. Fasting is defined as nothing to eat for at least 4-6 hours before blood draw.

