During the first cycle of TAK228, the following laboratory studies should be performed on day 15 (within 3 business days) - CBC with differential, Serum chemistries - Na, K, Cl, CO2, BUN, Cr, Ca, Mg, phosphorus, total protein, albumin, alkaline phosphatase, AST, ALT, total bilirubin, uric acid, and LDH, and a fasting serum glucose, triglycerides, cholesterol panel. Fasting is defined as nothing to eat for at

least 4-6 hours before blood draw.

Hemoglobin A1c should be obtained prior to cycle 1 day 1, cycle 3 day 1, cycle 6 day 1, cycle 9 days 1 and cycle 12 day 1.

An electrocardiogram will be obtained pre-dose (within 28 business days) prior to start of cycle 1 and within 3 days of starting each subsequent cycle.

The following staging studies should be performed at completion of 2 cycles of TAK228 (within 5 business days prior to starting cycle 3) – CT scans of neck, chest, abdomen, and pelvis; Chest X-ray – PA and lateral; and unilateral bone marrow biopsy and unilateral aspirate if bone marrow is involved with lymphoma at baseline. An optional PET/CT scan may be obtained at completion of 2 cycles of TAK228 at the discretion of the treating physician.

The following staging studies should be performed at completion of every 2 cycles beyond the first 2 cycles of TAK228 (i.e., +/- 5 business days prior to starting cycle 5, 7, 9, and 11): CT scans of neck, chest, abdomen, and pelvis; Chest X-ray – PA and lateral; and optional unilateral bone marrow biopsy and unilateral aspirate if bone marrow is involved with lymphoma at baseline at the discretion of the treating physician; An optional PET/CT scan may be obtained at completion of every 2 cycles of TAK228 at the discretion of the treating physician, but should be considered if previously FDG avid lymph nodes remain enlarged on CT imaging or physical examination.

In consenting patients, for correlative studies, a 10 ml of blood sample [1 heparin containing green top tube and 1 purple top tube (5 ml/tube)] will be collected at each of the following time points: cycle 1 day 1 (2-4 hours after dose), and cycle 2 day 1 (2-4 hours after dose). These samples will be transported within 4 hours (+/- 2 hours) of collection to the RPPA Core Laboratory Facility and/or Lymphoma Tissue Bank, depending on time of collection, at M. D. Anderson Cancer Center (MDACC). Blood from green top tubes will be processed for isolation of peripheral blood mononuclear cells (PBMC) using standard laboratory protocols.

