#### **Evaluation At Completion of Study**

Patients will be evaluated by the treating physician and a relevant history and physical examination, including performance status evaluation and vital signs, will be recorded 1 week (+/- 7 business days) after completion of TAK228. Toxicities will be graded according to the NCI CTC v4.0 during this visit.

The following laboratory studies should be performed 1 week (+/- 7 business days) after completion of TAK228 – CBC with differential, Serum chemistries - Na, K, Cl, Glucose, CO2, BUN, Cr, Ca, Mg, phosphorus, total protein, albumin, alkaline phosphatase, AST, ALT, total bilirubin, PT/PTT/INR, urinalysis, uric acid, LDH, and quantitative immunoglobulins, and a fasting serum glucose, triglycerides, and cholesterol panel. In addition, an EKG should be performed 1 week (+/- 7 business days) after completion of TAK228. Fasting is defined as nothing to eat for at least 4-6 hours before blood draw.

The following staging studies should be performed 2 weeks (+/- 14 business days) after completion of TAK228 – CT scans of neck, chest, abdomen, and pelvis; Chest X-ray – PA and lateral; and optional bilateral bone marrow biopsy and unilateral aspirate if bone marrow is involved with lymphoma at baseline at the discretion of the treating physician. An optional PET/CT may be performed 2 weeks (+/- 14 working/business days) after completion of TAK228 at the discretion of the treating physician.

For correlative studies, 10 ml of blood sample [2 heparin containing green top tubes (5ml/tube)] will be collected when a patient is taken off study (+/- 14 business days). These samples will be transported within 6 hours of collection to the RPPA Core Laboratory Facility and/or Lymphoma Tissue Bank, depending on time of collection, at M. D. Anderson Cancer Center (MDACC). Blood from green top tubes will be processed for isolation of peripheral blood mononuclear cells (PBMC) using standard laboratory protocols.

Patients will be evaluated by the treating physician and a relevant history and physical examination, including performance status evaluation and vital signs, will be recorded 1 week (+/- 7 business days) after completion of TAK228. Toxicities will be graded according to the NCI CTC v4.0 during this visit.

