The following laboratory studies should be performed 1 week (+/- 7 business days) after completion of TAK228 – CBC with differential, Serum chemistries - Na, K, Cl, Glucose, CO2, BUN, Cr, Ca, Mg, phosphorus, total protein, albumin, alkaline phosphatase, AST, ALT, total bilirubin, PT/PTT/INR, urinalysis, uric acid, LDH, and quantitative immunoglobulins, and a fasting serum glucose, triglycerides, and cholesterol panel. In addition, an EKG should be performed 1 week (+/- 7 business days) after completion of TAK228.

The following staging studies should be performed 2 weeks (+/- 14 business days) after completion of TAK228 – CT scans of neck, chest, abdomen, and pelvis; Chest X-ray – PA and lateral; and optional bilateral bone marrow biopsy and unilateral aspirate if bone marrow is involved with lymphoma at baseline at the discretion of the treating physician. An optional PET/CT may be performed 2 weeks (+/- 14 working/business days) after completion of TAK228 at the discretion of the treating physician.

For correlative studies, 10 ml of blood sample [2 heparin containing green top tubes (5ml/tube)] will be collected when a patient is taken off study (+/- 14 business days). These samples will be transported within 6 hours of collection to the RPPA Core Laboratory Facility and/or Lymphoma Tissue Bank, depending on time of collection, at M. D. Anderson Cancer Center (MDACC). Blood from green top tubes will be processed for isolation of peripheral blood mononuclear cells (PBMC) using standard laboratory protocols.

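### No pregnancy test is scheduled after the last dose: serum Beta-HCG is listed at screening and before each cycle but not in the end-of-treatment laboratory list

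*Combined protocol and SAP*

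**What the plan says.** Two laboratory lists include a pregnancy test. The Screening Evaluation list, introduced by "The following laboratory studies should be performed within 3 days prior to the first dose of TAK228", closes with "and urine analysis, and a fasting serum glucose, triglycerides, cholesterol panel, and serum Beta-HCG in women of child-bearing potential". The pre-cycle list in Evaluation During Study, introduced by "The following laboratory studies should be performed within 3 business days prior to each cycle of TAK228", closes with "and serum Beta-HCG in women of child-bearing potential".

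Two lists do not include one. The cycle 1 day 15 list ends with "uric acid, and LDH, and a fasting serum glucose, triglycerides, cholesterol panel". The list in Evaluation At Completion of Study, introduced by "The following laboratory studies should be performed 1 week (+/- 7 business days) after completion of TAK228", ends with "PT/PTT/INR, urinalysis, uric acid, LDH, and quantitative immunoglobulins, and a fasting serum glucose, triglycerides, and cholesterol panel". The completion text is printed twice and neither copy has the test.

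Inclusion criterion 3 requires women who could become pregnant to use two forms of contraception, or true abstinence, from consent until at least 90 days after the last dose.

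**The concern.** While a woman is on treatment, the plan does not rely on contraception alone. The test before each new cycle also checks the exposure of the cycle just finished. The last period of dosing is the exception: unless another pre-cycle draw happens to follow it, no scheduled test covers it. A woman who stops during cycle 1 has no scheduled test after her first dose, because the day 15 list omits the test as well.

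What is at stake is late recognition of a pregnancy conceived during final dosing. The plan itself treats the period after dosing as one of concern, since contraception continues for at least 90 days. The completion section also calls for CT of the abdomen and pelvis, nominally two weeks after treatment ends. The plan does not make that scan conditional on a pregnancy test, and its window overlaps the laboratory window. The scan is a reason the result would be useful, not evidence that a rule is broken.

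**Working it through.** The plan states no figure on this point to reproduce. The check is a comparison of the lists, followed by calendar arithmetic.

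**Step 1. The lists side by side**

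| Time point | Section | Timing | Beta-HCG |
|---|---|---|---|
| Screening | Screening Evaluation | up to 3 days before first dose | listed |
| Before each cycle | Evaluation During Study | up to 3 business days before | listed |
| Cycle 1 day 15 | Evaluation During Study | within 3 business days | absent |
| Completion (both copies) | Evaluation At Completion of Study | 1 week, plus or minus 7 business days | absent |

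Compared with the pre-cycle list, the completion list drops only direct bilirubin and Beta-HCG. It adds quantitative immunoglobulins and a glucose in the chemistry panel. Both copies read continuously, so no redaction or extraction gap accounts for the absence. The Safety Analysis section mentions only blood count, electrolytes, and kidney and liver tests.

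**Step 2. Inputs and assumptions**

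- Once-daily dosing and 28-day cycles come from Proposed Treatment/Study Plan. I assume dosing runs to day 28 and ignore public holidays.
- The outer limit of 3 business days is 3 to 5 calendar days, so a pre-cycle draw falls 0 to 5 days before day 1. For cycle 1 the tighter screening window gives 0 to 3 days.
- Day 1 to day 28 is 27 days.

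**Step 3. Time from last scheduled test to last dose**

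- Completed cycle, no further pre-cycle visit: 27 + 0 to 27 + 5 = 27 to 32 days. If only cycle 1 is given: 27 + 0 to 27 + 3 = 27 to 30 days.
- Stop on day *d*: (*d* − 1) + 0 to (*d* − 1) + 5 = *d* − 1 to *d* + 4 days. For *d* = 14 this is 13 to 18 days. In cycle 1 the upper limit is *d* + 2, so 13 to 16 days.
- Tested at the next pre-cycle visit, then stopped: the next day 1 is day 29, so the draw falls on days 24 to 29. That is from 4 days before to 1 day after a day-28 last dose.

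**Step 4. Does restaging guarantee the test?**

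The first restaging is due "within 5 business days prior to starting cycle 3". Five business days are 5 to 7 calendar days, against 3 to 5 for the pre-cycle laboratory window. A woman found to be progressing early in the restaging window could stop before the pre-cycle draw is due, so the test is not assured.

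**Step 5. What a completion-visit test would cover**

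Seven business days are 9 to 11 calendar days.

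- Earliest draw: 7 − 9 = −2 to 7 − 11 = −4, that is, 2 to 4 days before the last dose if the window is applied literally.
- Latest draw: 7 + 9 = 16 to 7 + 11 = 18 days after the last dose.
- A test on day 1 to day 18 after the last dose leaves 90 − 1 = 89 to 90 − 18 = 72 days of the contraception period untested.

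**The case against.** The strongest reply is that the schedule is coherent as written. Both scheduled tests come before dosing, which fits a purpose of checking before each new exposure; after the last dose there is no further exposure to check before. The documents do not require a post-treatment test, name no action that would follow a positive result, and already require contraception or abstinence for at least 90 days. The completion visit also includes a history and examination that might bring a pregnancy to light. One late test would not cover most of the 90 days, and the intervals above measure time since testing, not the probability of an undetected pregnancy.

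Much of this stands. It is why the point is minor and why no breach is claimed. It does not remove the gap: followed exactly, the schedule leaves some women's final exposure with no scheduled assay, although earlier cycles are followed by one. A history and examination are not a substitute.

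Two narrower objections are also fair. A draw before the last dose would contradict the requirement that it follow completion, so the early edge of the window is an ambiguity in wording rather than an instruction. From cycle 5 onward, restaging may fall on either side of the start of the cycle, so the mismatch in Step 4 is clearest at cycle 3. Finally, the document supplied is an abstract-style text; fuller protocol text might cover pregnancy testing, but that cannot be checked here.

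**Conclusion.** The point holds. Beta-HCG is scheduled at screening and before each cycle, is absent from cycle 1 day 15 and from both copies of the completion list, and is scheduled nowhere after treatment. For a woman with no further pre-cycle visit, the last scheduled test precedes the last dose by 27 to 32 days after a completed cycle (27 to 30 if only cycle 1 is given), and by less if she stops mid-cycle. These figures rest on daily dosing to day 28 and no public holidays; the omission itself rests on no assumption.

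Not every woman is affected, and the documents do not give the number of women of child-bearing potential, so no count can be stated. Nothing in the primary endpoint, sample size or Bayesian stopping rules changes. The point is an optional safety improvement.

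**What to change.** Add this item to the laboratory list in both copies of the Evaluation At Completion of Study text: *serum Beta-HCG for women of child-bearing potential, drawn after the last dose*. The final words settle the early edge of the window.

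The cost is one extra assay per eligible woman on blood already being drawn. No new visit is needed if the completion draw is placed after the last dose, within the existing window. The change has limits: a very recent conception could still be missed, and the remaining 72 to 89 days of the 90-day period would still depend on contraception or abstinence.

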##### Secondary Objectives

##### Phase II:

The secondary objectives of the Phase II portion of the trial are to define the safety & tolerability, progression free survival, duration of response, and overall survival of TAK228 in patients with relapsed lymphoma.

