**Accrual Comments:**

This is an open label, phase II clinical trial to evaluate the safety and efficacy of TAK228 in patients with relapsed lymphoma. The maximum sample size is 75 and the minimum samples size is 24 for Phase II.

**Is this an NCI-Cancer Therapy Evaluation Protocol (CTEP)?** No

**Is this an NCI-Division of Cancer Prevention Protocol (DCP)?** No

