Patients will be monitored by a cohort size of 5 after the first 15 patients according to the following stopping boundaries for OR at two cycles and reason for dose modification at one cycle. If the number of responses required for moving the trial to next stage has not been achieved, the patient enrollment will be halted until enough responses observed.

For cohorts I), TAK228 will be considered promising if it yields an OR rate of 45% at two cycles and a REASON FOR DOSE MODIFICATION rate of 25% at one cycle. A sample size of 25 ensures that, if the cohort is not terminated early, a posterior 90% credibility interval for overall response rate will have width of 0.310 at most, under the assumption of a 45% of OR rate. The prior probabilities of OR and REASON FOR DOSE MODIFICATION for the experimental regimen are modeled by beta distributions ( $Beta(0.9,1.1)$  and  $Beta(0.5,1.5)$ , respectively). Denoting probabilities of OR rate and REASON FOR DOSE MODIFICATION rate by ( $p_{OR}$ ,  $p_{Reason\ for\ dose\ modification}$ ), the following decision criteria will be applied: Stop the trial if  $Prob(p_{OR} < 45\% \mid data) > 0.95$  or  $Prob(p_{Reason\ for\ dose\ modification} > 25\% \mid data) > 0.95$ .

Patients will be monitored by a cohort size of 5 after the first 15 patients according to the following stopping boundaries for OR at two cycles and REASON FOR DOSE MODIFICATION at one cycle. If the number of responses required for moving the trial to next stage has not been achieved, the patient enrollment will be halted until enough responses observed.

Patients who are treated on study and have at least 1 disease restaging study prior to termination of study participation will not be replaced with an additional patient added to their disease cohort. Patients who are treated on study and fail to have at least 1 disease restaging study prior to termination of study participation will be replaced with an additional patient added to their disease cohort at the discretion of the principle investigator.

The duration of the study as a whole is defined first patient to start the screening period to the last patient to conclude their therapeutic period. The anticipated accrual is 3 patients per month on this trial. Thus, accrual for the study is expected to be complete in approximately two years. The total duration of the study is anticipated to be approximately three years.

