### Analysis Plan

For each patient cohort, summary statistics will be provided for continuous variables such as age. Frequency tables will be used to summarize categorical variables such as gender, histology, response, toxicity type and severity. Logistic regression will be utilized to assess the effect of patient prognostic factors on the response rate and the toxicity rate. The distribution of time-to-event endpoints, such as time to progression and overall survival, will be estimated using the method of Kaplan and Meier. Comparison of time-to-event endpoints by important patient characteristics will be made using the log-rank test.

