### Efficacy Analysis

Summary statistics will be provided for continuous variables. Frequency tables will be used to summarize categorical variables. Logistic regression will be utilized to assess the effect of patient prognostic factors on the response rate and the toxicity rate. The distribution of time-to-event endpoints, such as overall survival, progression free survival, and response duration, will be estimated using the method of Kaplan and Meier. Comparison of time-to-event endpoints by important subgroups will be made using the log-rank test. Cox proportional hazard regression may be employed for multivariate analysis on time-to-event outcomes.

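### Overall survival is a secondary objective, but no vital-status follow-up is scheduled after the end-of-treatment scan and no censoring rule is given

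*Combined protocol and SAP*

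**What the plan says.** The Phase II secondary objectives are safety and tolerability together with "progression free survival, duration of response, and overall survival of TAK228 in patients with relapsed lymphoma". Statistical Considerations lists the same endpoints. Efficacy Analysis says that the distributions of time-to-event endpoints, "such as overall survival, progression free survival, and response duration, will be estimated using the method of Kaplan and Meier". Analysis Plan adds: "Comparison of time-to-event endpoints by important patient characteristics will be made using the log-rank test". Efficacy Analysis also allows a model: "Cox proportional hazard regression may be employed for multivariate analysis on time-to-event outcomes".

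Evaluation At Completion of Study lists what happens after treatment:
- a clinic, laboratory and EKG visit at 1 week (+/- 7 business days);
- imaging, under the sentence "The following staging studies should be performed 2 weeks (+/- 14 business days) after completion of TAK228";
- a correlative blood sample when the patient is taken off study. The text does not say whether that is the same event as completing TAK228.

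The last paragraph of Phase II design defines the duration of the whole study as running from "first patient to start the screening period to the last patient to conclude their therapeutic period". It expects accrual in about two years and a total of about three. No section names a survival contact, a source of vital status or a censoring rule for any time-to-event endpoint.

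**The concern.** Kaplan-Meier estimation assumes that patients censored at a given time have the same future risk as those still followed. If the scheduled contacts are the data source, a patient who stops TAK228 alive leaves the OS risk set within about five weeks. In relapsed lymphoma, stopping treatment is usually related to prognosis. That is an inference, because the supplied text gives no discontinuation criteria.

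The curve would then mainly describe mortality on treatment and just after it, and would usually lie above true survival. It would lie below if death were less likely after treatment than on it. Log-rank and Cox comparisons would be biased where stopping patterns or post-treatment risk differ between subgroups. Where they do not differ, the log-rank test keeps its level but has few deaths to work with. Vital status that was never collected may not be recoverable at analysis, so this is more than a missing detail of method.

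**Working it through.** **The plan's own timeline.** 75 patients / 3 per month = 25 months of accrual, against about two years stated. No maximum treatment length is given. The last time point named is cycle 12 day 1, so I assume 12 cycles: 12 x 28 / 30.4375 = 11.04 months. Then 25 + 11.04 = 36.0 months, against about three years stated. On that reading, no time is set aside to follow the last patients.

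**Last dated contact.** Two weeks is 14 days. Fourteen business days span up to 20 calendar days. The limit is 14 + 20 = 34 days = 4.9 weeks, or L = 1.12 months. The nominal two weeks gives L = 0.46 months.

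**Model (all hazards assumed).** Treatment ends at rate λ = ln2 / m_T, where m_T is the median treatment time. A share q of those ends are deaths, so the on-treatment death hazard is λ_d = qλ. The post-treatment death hazard is λ_p = ln2 / m_P, where m_P is the median survival after treatment. Up to the 12-cycle cap:
- True OS: S(t) = exp(-λt) + (1-q)λ[exp(-λ_p t) - exp(-λt)] / (λ-λ_p).
- Recently stopped patients per on-treatment patient in the risk set: R = (1-q)λ[exp((λ-λ_p)w) - 1] / (λ-λ_p), with w = min(t, L).
- Hazard that Kaplan-Meier sees: h = (λ_d + λ_p R) / (1 + R). The estimate tends to exp(-∫h).

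**One case:** m_T = 4 months, m_P = 12 months, q = 10%. Then λ = 0.1733, λ_p = 0.0578, λ_d = 0.0173.
- True 11-month OS = 0.1486 + 1.350 x (0.5297 - 0.1486) = 0.663.
- L = 1.12: R = 0.186, cumulative hazard 0.257, estimate exp(-0.257) = 0.773, error +11 points.
- L = 0.46: R = 0.074, cumulative hazard 0.2205, estimate 0.802, error +14 points.

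**Grid.** m_T = 2, 4, 6 months; m_P = 6, 12, 24 months; q = 5, 10, 20%; two values of L: 54 scenarios. The ratio of on-treatment to post-treatment death hazard is q x m_P / m_T.

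| Scenarios | Error in 11-month OS (points) |
|---|---|
| Ratio at most 1 (46) | +1.3 to +32.4 |
| of these, m_P = 6 months | +7.9 to +32.4 |
| of these, m_P = 12 months | +5.4 to +18.3 |
| of these, m_P = 24 months | +1.3 to +8.6 |
| Ratio 1.2 or 2.4 (8) | -14.6 to about -1.5 |

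Scenario counts are not probabilities. In the 46 scenarios, 5-29% of patients have an observed death, which is about 4 to 22 of 75. For scale, the sampling SD of the 11-month estimate with full follow-up is 4-6 points with 75 patients and 7-11 with 25.

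**A second model.** Here treatment stops at progression (median 3 or 6 months) or at 11 months, and median survival after progression is 4, 8 or 16 months. True 11-month OS is 33-76%, and Kaplan-Meier from scheduled contacts gives 62-87%. The error is +8 to +41 points with about 5-15 deaths seen among 75 patients. The direction agrees; the size depends on the assumptions.

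**PFS.** If 10-30% of patients stop before progression, the error is within 0.1 point when stopping is unrelated to prognosis, and about -6 to +6 points when the hazard after stopping is 0.5 to 3 times that on treatment (scan interval ignored).

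**The case against.** The strongest reply is that absence here proves little. The text is headed as an abstract, cites a numbered reference without a list, and contains neither discontinuation criteria nor endpoint definitions. Survival follow-up normally sits beside such criteria. The trial runs at one centre, so later deaths may be known from its records. The study-duration sentence stands in a paragraph about accrual time and is not called a data cut-off. All of this stands, and it is why the point is conditional. It does not remove the gap: no section names records as the source of vital status or says at what date OS is censored, and if that is the intention, writing it down is most of the fix.

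Three stronger readings are tempting and are not supported:
- A reader might infer that the plan censors OS at the last visit, so that bias is certain. No section says so.
- A reader might infer that follow-up would make the OS comparisons well powered. Power is about 97% for 75 pooled patients with post-treatment medians of 6 versus 24 months (treatment median 4 months, 10% of treatment ends being deaths). But the plan runs three parallel cohorts of at most 25, and Analysis Plan works by cohort. In 25 patients, at an assumed 1 per month, power with follow-up is about 50% for that fourfold contrast and 15-20% for a twofold one. For twofold contrasts in 75 patients it is 42-54%. No OS comparison in the plan is powered.
- A reader might infer that PFS and response duration fail in the same way. They are captured through the end-of-treatment scan; the gap concerns only patients who stop without progression, including responders.

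**Conclusion.** The point holds as a conditional one. As written, the schedule supports OS only to about 34 days after treatment, and nothing in the supplied text extends it. If the scheduled contacts are the data source, the OS curve would usually be too high, by roughly 1 to 32 points at 11 months where death is at least as likely after treatment as on it. It could be up to about 15 points too low where death is likelier on treatment. These ranges rest on assumed exponential hazards and the assumed 12-cycle cap; the documents give no event rates against which to narrow them. In many scenarios the error exceeds the sampling SD, and more patients would not reduce it.

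OS is a secondary endpoint in a non-randomised trial. The response endpoint and the stopping rules do not depend on it. The change should be made, but the trial's main conclusion does not hang on it.

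**What to change.** - **Evaluation At Completion of Study:** add vital status and the date of progression or next therapy, by record review or telephone, about every 3 months after treatment ends. Add one vital-status check of all patients at a common cut-off date.
- **Phase II design, study-duration sentence:** name that cut-off as the end of outcome follow-up. It can be the date on which the last patient concludes therapy, so the study need not be longer. State that earlier patients are followed to it after their own treatment ends.
- **Efficacy Analysis:** censor OS at the date last known alive, and PFS and response duration at the last adequate disease assessment.
- **State the limit:** follow-up of the last-enrolled patients will be short. With 75 patients and assumed treatment medians of 2-6 months, the shortest follow-up averages about 7-10 months, and about 2-13 patients fall below 11 months.

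In the 46 scenarios above, this brings the 11-month OS error to within 0.4 points with 75 patients, 0.6 with 45 and 1.2 with 24. The two smaller sizes are the minimums given in Estimated Accrual and Accrual Comments.

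The cost is a short amendment and modest record-review or telephone work at one centre for up to 75 patients, with no added visits or procedures. It assumes that consent covers contact or record review after treatment; the consent pages were not supplied, so this must be checked. If follow-up is not wanted, remove OS as an objective and label PFS and response duration as observed through the end-of-treatment scan only.
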